Imaging Parameters (sessions 3 and 4). Scanning will take place at the Center for Biomedical Imaging on the Siemens 3T Prisma. Functional and structural scanning parameters are detailed in the **NI Core**. High-resolution structural, fluid-attenuated inversion recovery (FLAIR), diffusion-weighted (DWI), and arterial spin labeling (ASL) perfusion imaging will use in-house standard sequences and will be collected from all participants in session 3. The task-based fMRI sequence will be optimized for an event-related design with a TR of 2 seconds. For the resting-state data, a TR of 0.8 seconds will be used. Task-based and resting-state imaging will be collected in session 4 with varying protocols for participants of SG and CG as described in the timeline below and explicitly detailed in the information and consent form. All MRI sequences will be accompanied by electrical recording of physiological signals from the upper body (e.g., electrocardiogram, electrodermal analyses) to support processing of MRI data and for secondary analyses examining relationships between autonomic nervous system dysfunction, brain, and behavioral outcomes.

D2. TIMELINE

Participants of both groups (stroke, control) will undergo the same protocol, which includes 4 sessions (outlined in the table below).

Session Number	Task Description	Location at Medical University of South Carolina	Approximate Time Commitment
0	Telephone Eligibility Screening 
 • Sensorimotor function screening (Appendix 1) • Cognitive screening (TICS^{26,27}) • MRI Safety Screen 	Via telephone	30 minutes
1	Consent	Stroke Recovery Research Center or remotely through electronic consent	20-30 minutes
2	Multi-system Assessment 
All participants
 
 • Pregnancy Test • EHI[§] • Questionnaires (Appendix 2)[§] • Neuro-Cognitive and emotion Assessment 
Stroke group
 
 • physical Assessment of upper-extremity sensorimotor functioning • NIH-SS 	Stroke Recovery Research Center or partly remotely [§]	3 – 3.5 hours

	
 • SIS[§] 		

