3	
MRI scanning and task familiarization
 
 • MRI Safety Screen • Sleep and vigilance screening 
MRI sequences:
 
 • FLAIR • DWI • ASL • T2* weighted sequence (resting-state) • Physiological recordings 
Learning task:
 
 • Task familiarization (in the mock scanner) 	Center for Biomedical Imaging	2 – 2.5 hours
4	
MRI scanning during task practice
 
MRI Safety Screen
 
Sleep and vigilance screening
 
MRI sequences:
 
 • High-resolution T1 weighted • T2* weighted sequence (task-based) during task practice • Physiological recordings 	Center for Biomedical Imaging	2 – 2.5 hours

D3. DATA ANALYSIS

D3.1 Sample Size Justification.

Given the scarcity of pilot data on stroke and control participants and fMRI-based dynamic connectivity during motor learning, justification has to be based on our best estimates and regarded with some caution. One of the primary goals of this project is to determine effect sizes for the follow-up grant proposal. For changes to latent connectivity characteristics induced by implicit motor learning (pre/post evaluation), empirically obtained effect size estimates were derived from the average effect size of published studies involving participants with chronic stroke⁹ and healthy volunteers⁵⁰. Consequently, sample sizes of 25 and 15 in the stroke survivors and healthy volunteers will allow us to estimate the for the main effect of time (pre/post learning) the within-group effect sizes can be expected to be in the range of 0.33 - 0.52 at 90% confidence level.

D3.2 Analysis Plan.

Imaging Preprocessing. Data will be processed by the CBI Computational Core led by [name]. Preprocessing parameters for the task-based fMRI data will be optimized to fit the requirements of the representational similarity analysis (RSA, described below), specifically smoothing will be reduced to allow for better multivariate pattern detection. Resting-state fMRI data will undergo in-house standard preprocessing.

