There is a relatively equal ratio of male to female stroke patients in South Carolina. In the duration of this project, forty (N=25 stroke group, N=15 control group) individuals will be enrolled. Consequently, 50% women will be assigned to each group. There will be no exclusion criteria with respect to ethnic background. Demographic data from the US Census Bureau (2016 estimates.) indicates the sex, race and ethnicity distribution in South Carolina as follows: 51.5% female, 48.5% male; 68.5% white persons not of Hispanic origin, 27.5% Black or African American, 0.5% American Indian and Alaska Natives, 1.6% Asian persons; with 5.5% persons of Hispanic origin. The goal in the proposed study is to construct a participant pool that matches population proportions in South Carolina. (2016; <https://www.census.gov/quickfacts/SC>). Consequently, we will seek to enroll a minimum of 31.5% minority representation per group. As necessary, advertisements will be placed in newspapers and radio stations with primarily African-American or Hispanic readership and audience.

Comfort and reliability considerations:

During the administration of some of the neuropsychological assessments, the participants' verbal responses will be audio recorded for quality control purposes.

- Video recording of sensorimotor functional tests

During all in-person sessions, snacks and water will be offered between testing administrations in order to improve energy, limit fatigue, and promote comfort. Furthermore, multiple breaks will be offered.

Finally, participants will be given the option to schedule sessions on the same day, with a break, if additional visits/travel would be burdensome.

b. Sources of Materials

Data collected from all participants will include responses to diagnostic interview, neuropsychological assessment, questionnaire responses, structural and functional brain images, behavioral performance from scanner tasks, heart rate, respiration, demographic information, health/medication information (to determine experiment counter-indicators), contact information for scheduling appointments, personal address and other information for processing payment, and related information for the sole purpose of research and ensuring participant safety. Additionally, consent forms and HIPAA forms will be collected.

c. Potential Risks

Risks of in-person visits due to COVID-19

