The option to remotely complete some of the sub-tests of the multi-system assessment (session 2), as for example the MoCA, the Stroke Impact Scale, the Edinburgh Handedness Inventory, and the BDI will be given to participants if they are unable to physically come to the Stroke Research Center for the time being, such as due to COVID19 precautions. Phone calls or video conferencing through Microsoft Teams, Zoom (with HIPAA approved license using single sign-on, or Doxy.me will be utilized to properly administer and oversee the completion of these assessments.

MRI risks.

There is a serious risk that MRI could move iron-containing objects in or around the face or head, which could in the process possibly harm the person. As such, these contraindications will be thoroughly screened at intake and at each scan. Participants are thoroughly screened to prevent metal being brought into the MR environment and are asked to change clothes into MR safe (no zippers, buttons, etc.) clothing before entering the MR chamber. In

the absence of risks related to metal, exposure to magnetic field strengths used in the present study is not shown to be a significant health risk. Electrodes used for physiological recordings are MRI safe, however may result in mild irritation to skin at the placement sites where adhesive is present.

Risks to an unborn fetus from exposure to the MRI field strength used in the proposed research (3 Tesla) are unknown. Therefore, pregnant females and those who may become pregnant (unwilling to follow study restrictions limiting chances of conception) will not be allowed to participate. Participants will be asked to lie still and awake for up to 1.5 hours in the scanner and this can occasionally result in soreness, stiff back, etc. Participants will be queried approximately every 10 minutes about their comfort. All investigators and research assistants running participants in imaging center are thoroughly trained in MR safety yearly as a requirement to run scans.

Claustrophobia.

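### The only listed pregnancy test is in a session without MRI, with no limit on the time to the scans; moving it to the first scan day is a cheap improvement

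*Combined protocol and SAP*

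**What the plan says.** Section D1.3 lists pregnancy among the exclusions for all participants and gives the unknown fetal effect of MRI as the reason. Section E1.c (MRI risks) repeats this for the 3 Tesla field and sets the rule: "pregnant females and those who may become pregnant (unwilling to follow study restrictions limiting chances of conception) will not be allowed to participate". The conception restrictions are not described further.

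The D2 timeline lists "Pregnancy Test" once, under all participants in session 2, the multi-system assessment. That session has no MRI sequence, and its location is "Stroke Recovery Research Center or partly remotely". The test does not carry the mark that the table puts on the handedness inventory, the questionnaires and the stroke impact scale, so it appears to be an in-person item.

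The scans are in session 3 ("MRI scanning and task familiarization") and session 4 ("MRI scanning during task practice"). Each lists an MRI safety screen, and neither lists a pregnancy test. Section E2.b says that MRI eligibility is checked at first telephone contact, at intake and again at every scan. It also makes the coordinator responsible for eligibility throughout the study. Section E1.a lets participants combine sessions on one day if travel is a burden.

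**The concern.** The exclusion exists to prevent exposure in the scanner, so the status that matters is the status at the scan. Pregnancy can begin between visits, and the one objective check the plan names is attached to a visit where there is no exposure. Without a limit on the interval, a negative result at session 2 may be out of date by session 3, and more so by session 4.

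At stake is participant safety. A woman who conceives after session 2 despite the restrictions, and does not know it, could be scanned although the plan means to exclude her. No estimate, comparison or aim of the study depends on this.

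**Working it through.** There is no figure in the plan to reproduce. The check sets the sections side by side and then works out the planning numbers for the fix.

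**Where the test and the exposure fall (section D2)**

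| Session | MRI scan | Pregnancy test listed | MRI safety screen listed | Time |
|---|---|---|---|---|
| 0 (telephone) | no | no | yes | 30 min |
| 1 (consent) | no | no | no | 20–30 min |
| 2 (assessment) | no | yes | no | 3–3.5 h |
| 3 | yes | no | yes | 2–2.5 h |
| 4 | yes | no | yes | 2–2.5 h |

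The table therefore has one test, and none in either of the two scan sessions.

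**Interval from test to scan.** Neither D1.4 nor D2 sets a maximum, and E2.b allows sessions to be rescheduled. The only day limit in the document is 30 days in D1.4. It governs the reuse of standardized assessments and questionnaires from another study, not the time from the pregnancy test to a scan.

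**When same-day scheduling closes the gap (D2 times, breaks not counted)**
- Session 2 result current for session 3: both on one day, 3 + 2 = 5 h to 3.5 + 2.5 = 6 h.
- Session 2 result current for both scans: all three on one day, 3 + 2 + 2 = 7 h to 3.5 + 2.5 + 2.5 = 8.5 h, less if parts of session 2 are done remotely.
- One test on the day of session 3 covering both scans: sessions 3 and 4 on one day, 2 + 2 = 4 h to 2.5 + 2.5 = 5 h.

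Combining sessions is the participant's option, so none of these can be assumed for everyone.

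**What the scan-day screen covers.** In D1.3 pregnancy is excluded only on account of MRI. E2.b has MRI eligibility screened at every scan. Together these make a pregnancy question at sessions 3 and 4 likely. The screen's content is not given, however, and the sentence in E1.c that "these contraindications will be thoroughly screened at intake and at each scan" follows a description of iron-containing objects. A question can identify a known pregnancy but not an unrecognised one.

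**Planning numbers.** The main study has 25 + 15 = 40 participants (D1.1). E1.a states that "50% women will be assigned to each group".
- Women, if that target is met: 40 × 0.5 = 20.
- Scan sessions among them: 20 × 2 = 40.
- Extra kits if the test is moved: 0.
- Extra kits if it is also repeated before session 4: at most 1 per woman who can become pregnant, so from 0 (sessions 3 and 4 always on one day) to about 20 (all 20 women can become pregnant and all attend on separate days).

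The 20 is not a maximum. The same section aims to match a state population that is 51.5% female, which gives 40 × 0.515 = 20.6, and nothing caps the number of women. Fewer than 20 are likely to be able to become pregnant, because D1.2 sets no upper age limit. Pilot volunteers are left out, since the document does not say which sessions they attend.

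The number of pregnancies that could be missed cannot be computed. The interval, the share of women who can become pregnant, and the content of the restrictions are all absent.

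**The case against.** The strongest reply is that pregnancy is already checked on scan days. It is an MRI-eligibility criterion in this protocol, and MRI eligibility is screened at every scan. This largely stands. A reader might infer from the D2 table that pregnancy goes unscreened at sessions 3 and 4, and the document does not support that. It supports only the narrower statement that no test is listed there.

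A second reply is that a summary table is weak evidence of absence. Imaging procedures are said to be "explicitly detailed in the information and consent form", and that form is not in the reviewed text. It, or the imaging center's own practice, may already require a scan-day test. This stands as a limit on what can be concluded. If so, D2 needs only a line saying it.

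A third reply is that the remaining case is narrow and the remedy partial. It takes a conception despite the restrictions, after a negative test, and unrecognised by the woman. If the sessions are close together, most such conceptions would be too early for any test to show. This also stands: the fix helps mainly when the interval is long. The document permits a long interval but does not show that one is usual.

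A fourth reply is that moving the test gives up an early eligibility check. That is a real cost and is counted under the fix.

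None of these removes the mismatch between the stated time of the test and the time of the exposure it guards against.

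**Conclusion.** The point holds as a cheap improvement to participant safety. D2 places the only listed pregnancy test in a session without MRI, and nothing limits the time to the scans in sessions 3 and 4. A pregnancy that begins after session 2 and is unrecognised by the woman could be missed.

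The risk is small: the conception restrictions, the scan-day screen, the coordinator's eligibility duty and the option of same-day sessions all reduce it. Its size cannot be derived from the document. A reader might take 20 women and 40 scan sessions as an upper bound or as a measure of risk. They are neither, being planning figures that follow from a 50% enrolment target in the main study.

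The conclusion assumes that the scan-day screen asks about pregnancy but does not test for it, and that the unseen consent form requires no scan-day test. The aims, estimates and statistical analysis are unaffected.

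**What to change.** In the D2 table, move the pregnancy test for women who can become pregnant from session 2 to the day of session 3, before scanner entry. One test then covers both scans if session 4 is on the same day. If session 4 is on a different day, repeating the test before that scan is optional.

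Moving the test adds no kits. The repeat adds one kit per such woman, about 20 at most under the planning figures above and probably fewer. E2.b mentions restrooms near the imaging center's waiting area, so a urine kit would be practical there (the type of test is an assumption).

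The cost is that a pregnancy would be found only after the 3 to 3.5 hours of session 2. A sponsor who wants to avoid this can keep the session 2 test and add the one at session 3, at one extra kit per such woman. A very early conception could still be missed under any of these schedules. The statistical analysis needs no change.

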Appendix 1: Pre-Screening Telephone Questionnaire.

Appendix 2: Demographic, Education, Medication Questionnaire.
